4 METHODS

Performance will be clinically measured using the Knee Society Score (Ewald, 1989; appendix 2). As part of the KSS flexion will be measured, both passive and active. The measurement will be done by a physiotherapist. Like the patient the physiotherapist will be blinded for the treatment.

The Chair Raise test(standing up from a firm straight-backed chair keeping the arms folded across the chest) and stair climb test(ascending a flight of eleven 17.8 cm tall steps with an 30 cm tread depth, use of one hand rail is allowed) is combined with a 10 point VAS measurement of anterior knee pain(McCormack et al., 1988). This consists of a pain scale from 0 to 10 on which the patient can point to the amount of pain (0 means no pain, 10 means the worst possible pain) Recording of the nature and incidence of all intra-operative and post-operative complications will be the method to assess safety. The difference between computer navigation measurements of leg axis and range of motion and clinical and X-ray measurements of these parameters will be evaluated. For this evaluation the pre-op standard X-rays and the per-operative computer navigation data will be used.

The relation between patella tilting and post-operative pain will be measured during functional tests Stair climb and chair raise according to a Visual analog scale (VAS) .

Patellar tilting will also be assessed on consecutive X-rays by the orthopaedic surgeon.

A WOMAC patient questionnaire (appendix 3) will be done to evaluate the patient's opinion on recovery, post-operative pain, and function(Bellamy et al., 1988).

An EQ-5D patient questionnaire (appendix 3) will be done to evaluate the patient's opinion of their health status (mobility, self-care, usual activities, pain/discomfort, anxiety/depression and a visual analog scale (VAS) to measure the patient's self-rated health outcome).

All evaluations will be conducted on the follow up moments mentioned in the follow up table

at page 8.

The prostheses used in this study both have a CE mark. All information concerning these prostheses is attached as appendix 4

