The purpose of this investigation is to primarily compare the post-op function recovery of and complications of patients who received a Scorpio PS or Scorpio NRG PS design. A secondary purpose is to compare anterior knee pain, patella tracking and patella tilting between these two groups.

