9.1.3 At Discharge(clinical researcher)

- Date of discharge
- Mobilisation figures (date out of bed and date mobilisation)
- Complications
- Active Range of Motion
- X-graph post-op evaluation

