9.1.4 Post-operative Evaluation

Patients will be assessed at post operative intervals at 6 weeks 3 months, 6 months 1, 2 and 5 years.

Post-operatively

- **Clinical Evaluation(*physiotherapist*)**
 - Date of assessment
 - Complications
 - Knee Society Score Evaluation
 - Pain
 - Walking
 - Stairs
 - Support
 - Flexion Contracture
 - Extension Lag
 - Range of Motion (active and passive)
 - Stability-anterposterior
 - Mediolateral stability
 - Patella tracking
 - Chair raise test, stair climb test
 - WOMAC, EQ-5D patient evaluation questionnaires

- **Radiographic Evaluation(*clinical researcher*)**

- Date of graphs taken
- AP and Lateral view
- Radiolucencies
- Patella tilt

9.2 *Adverse event/ Complications (surgeon)*

- Intra-operative and post-operative complications
- Date of event/complication
- Local complications
- Mechanical complications
- Revision required
- General complications
- Outcome complication

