16 RISK BENEFIT ANALYSIS

16.1 Risk

The Scorpio PS knee prosthesis is standard used for total knee arthroplasties in the AZM. During the 10 years experience with the Scorpio PS no additional complications have been seen. The Scorpio NRG PS has evolved from the the Scorpio PS. In basis both prostheses are

the same, only the tibial insert has changed and the femoral component has a slightly different shape. No additional risks for the use of the Scorpio NRG knee prosthesis are expected but still need to be proven. As in any surgical procedure, certain risks are associated with total knee arthroplasty. These risks include but are not limited to: anaesthetic and post-anaesthetic reactions (such as hyperaemia), allergic reactions to prophylactic antibiotics or blood transfusions, damage to blood vessels or nerves, patella, femoral or tibial fractures during implantation, perforation of the cortical wall, or death. Post-operatively, a patient may experience thrombophlebitis, pulmonary embolus, dislocation, pain, limp, component loosening, or the need for additional surgery.

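### Patellar tilt is compared between arms, but no masking is stated for its reading, and Sections 4 and 9.1 name different readers

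*Combined protocol and SAP*

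**What the plan says.** The last paragraph of the introduction states: "A secondary purpose is to compare anterior knee pain, patella tracking and patella tilting between these two groups". Section 3 adds the relation between tilt and post-operative pain, and a secondary hypothesis of no difference in complications.

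Three places assign the tilt reading:
- Section 4: "Patellar tilting will also be assessed on consecutive X-rays by the orthopaedic surgeon".
- Section 9.1.1 (pre-operative): tilt is listed under the radiographic evaluation, assigned to the clinical researcher.
- Section 9.1.4 (post-operative): tilt is again listed under "Radiographic Evaluation(*clinical researcher".

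Three places assign complications:
- Section 9.1.3: an item under "At Discharge(clinical researcher".
- Section 9.1.4: an item at each follow-up under "Clinical Evaluation(*physiotherapist".
- Section 9.2: "Adverse event/ Complications (surgeon", including mechanical complications and whether revision was needed.

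On blinding, Section 2.2 says the patient is not told which implant was placed, and Section 4 blinds the patient and the physiotherapist. No other role is described as blinded. No section describes masked films, independent reading or masked classification of events. Section 2.3 gives all clinical measurements to the clinical researcher, whereas Section 4 has the blinded physiotherapist measure flexion.

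**The concern.** The protocol saw the need for a blinded assessor of flexion but did not carry the precaution over to tilt, which it also compares between arms. The surgeon places the implant and records it among the operative data (Section 9.1.2), so cannot be blind for a patient he or she operated on. If knowledge of the arm shifts the reading, the shift goes straight into the estimated difference, and the t-test in Section 14.1 cannot separate it from a device effect.

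Naming two readers is a separate problem. If both read films, differences between them add noise. They can also distort comparisons over time if one reads early films and the other late ones, and comparisons between arms if the choice of reader is related to the arm.

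For complications, whether an event counts as local, mechanical or device-related involves judgement. Section 9.2 gives that to the surgeon with no masking stated. The hypothesis is no difference, so differential classification could create a difference or hide one.

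**Working it through.** **Assessor against blinding status, as written**
- Flexion and other clinical items: physiotherapist (Sections 4, 9.1.1, 9.1.4), blinded. Section 2.3 contradicts this by naming the clinical researcher.
- VAS pain, WOMAC, EQ-5D: reported by the patient, blinded.
- Tilt: orthopaedic surgeon (Section 4) or clinical researcher (Sections 9.1.1, 9.1.4). Blinding is not stated for either.
- Complications: clinical researcher at discharge, blinded physiotherapist at visits, surgeon in Section 9.2. The plan does not say which record supplies the comparison.
- Allocation list and envelopes: scientific researcher (Section 2.2). The documents do not say whether this is the same person as the clinical researcher.

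The gap for tilt therefore exists whichever section is followed, and it is most direct under Section 4.

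**The plan's own figure, used only to fix the group size**

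Section 6.1 gives a difference of 7 degrees, SD 11, 80% power and two-sided alpha 0.05. Normal approximation: n = 2 × (1.96 + 0.84)² × (11/7)² = 2 × 7.84 × 2.469 = 38.7, so 39 per arm. The t-based solution is 39.75, so 40 per arm, as stated. Then 80 × 1.10 = 88, also as stated.

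**Illustration of a reading shift in tilt**

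The documents give no tilt SD, so this is in SD units, assuming 40 readable patients per arm and no true difference.
- Standard error of a difference = √(2/40) = 0.224 SD.
- Shift that puts the expected result at p = 0.05: 1.99 × 0.224 = 0.445 SD. About half of such trials would be falsely significant.
- A shift of 0.2 SD: 0.2/0.224 = 0.894 standard errors. False-positive rate = P(Z > 1.96 − 0.894) + P(Z < −1.96 − 0.894) = 0.143 + 0.002 = 0.145, against the nominal 0.05.

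**Illustration for complications**

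Reclassifying one event in an arm of 40 moves that arm's rate by 1/40 = 2.5 percentage points; two events move it by 2/40 = 5 points.

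**Number of films**

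Table 2 schedules patella defile views pre-operatively, at 12 and 26 weeks, and at 1, 2 and 5 years: 6 per patient, at most 88 × 6 = 528.

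**The case against.** The strongest reply is that this is a drafting inconsistency about a minor outcome. The arm comparison of tilt rests on one sentence of the introduction. Section 3 mentions tilt only in relation to pain, and Section 14.1 lists patella tracking, not tilt. No directional hypothesis for tilt is stated; the expected reduction in ventral knee pain in the introduction concerns pain. The shift calculation would apply to any continuous outcome at this sample size. All of this stands. It limits the importance of the point but leaves the reading unmasked.

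A reader might also infer more than the documents support:
- *That only the physiotherapist's measurements are protected.* The patient is blinded too, which covers VAS pain, WOMAC and EQ-5D.
- *That the operating team makes all these judgements.* The clinical researcher is not described as operating or as knowing the arm, and Section 4 does not say that the film reader operated on the same patient, though that is the natural reading.
- *That the surgeon is the only source of complications.* Discharge and follow-up records exist, and Section 10 requires all operative-site and general medical complications to be documented, which limits discretion over occurrence.
- *That occurrence should therefore come from the blinded physiotherapist's record alone.* Those visits start at 6 weeks and have a gap from 2 to 5 years, so in-hospital and between-visit events could be missed, and classification would still lie with the surgeon.
- *That consecutive films are scored with earlier films in view.* The word may simply mean films from successive visits.

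**Conclusion.** The point holds in a limited form. No masking is stated for the reading of tilt, a compared outcome, and the named reader differs between Section 4 and Sections 9.1.1 and 9.1.4. For complications, the gap is that the surgeon's assessment is unmasked and the record used for the comparison is undefined. Neither affects the sample size or the patient-reported outcomes.

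The size of any bias is unknown. The figures of 0.45 SD, 14.5% and 2.5 to 5 points show how sensitive a trial of this size would be; they do not estimate bias in it. The conclusion assumes that the surgeon in Section 4 is, at least often, the one who operated.

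The conflict between Sections 2.3 and 4 deserves equal attention, because the blind on the primary flexion measurement depends on how it is resolved. This is a repair that should be made because it is cheap, not a fault that invalidates the design.

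**What to change.** 1. **Tilt.** Reconcile Sections 4, 9.1.1 and 9.1.4 to one reader from the staff already named, for example the clinical researcher. The reader must not have operated on the patient or hold the allocation list, so the protocol should say whether the clinical and scientific researchers are different people. That reader measures tilt on the scheduled patella defile films, labelled by study code only and cropped where possible, in random order across visits and arms, without access to the operative record.
2. **Complications.** Keep the discharge record, the physiotherapist's visits and the surgeon's record as joint sources of occurrence, and leave safety reporting unchanged. For the arm comparison, classify events by criteria fixed before data review, from descriptions with the implant type removed.
3. **Clinical measurements.** Resolve Section 2.3 against the blinded physiotherapist in Section 4.

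The cost is protocol wording, relabelling and cropping of at most 528 films, and preparation of event descriptions; no extra visits or films. It needs no extra staff if a named person meets the conditions in item 1. There are two downsides. Masking may be imperfect, since Section 16.1 says "only the tibial insert has changed and the femoral component has a slightly different shape" and a reader may recognise the component. Films are also read in batches rather than at the visit. Because Section 15 plans both a two-year and a five-year paper, two batches would serve: up to 88 × 5 = 440 films, then up to 88.

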5 INVESTIGATIONAL SITES

This study will be conducted at the Academic Hospital in Maastricht, the Netherlands.

6 SELECTION OF PATIENTS

6.1 *Number of patients*

The number of patients is based on average postoperative flexion as the primary endpoint. According to Morawa¹⁰ Scorpio patients showed a maximum post-operative flexion of 104 degrees. An increase in maximum flexion of 5 degrees is already noticeable for the patient, so clinically important. According to pre marketing results the Scorpio NRG PS knee prosthesis can reach a flexion of more than ten degrees extra compared to the Scorpio PS. For the primary endpoint we want to aim at an increase in maximum flexion of 7 degrees. According to Schouten¹² a sample size of 40 patients in each group is needed with a difference in flexion of 7 degrees, a standard deviation of 11^{7,8} a 80% power with a significance level (alpha) of 0.05 (two-tailed). When we take into account a lost of FU of 10% a total groupsize of 88 is anticipated.

6.2 *Patient selection criteria*

All patients on the waiting list for a total knee prosthesis at the department of orthopaedics at the AZM will be checked for suitability for this study. Patients will be verbally and in writing informed about the study during the first visit related to the TKP, and will be provided with the patient information. One week before surgery during a pre-operative visit the patients will be orally informed again, All questions about the study will be answered and the patient will be asked to participate in this study. If a completely informed patient wants to participate, the informed consent will be signed.

If a patient doesn't want to participate it is very likely that he will receive the Scorpio PS prosthesis since this is the standard used knee prosthesis at the AZM. If a patient does or doesn't want to participate has no effect on day of surgery or further medical care.

The confidentiality of the subject will be maintained at all times. The patient will be told that he/she is free to refuse the collection of his/her clinical data or to withdraw from the Investigation at any time without compromising future medical care.

TABLE 1. Patient Inclusion and Exclusion Criteria

Inclusions

- Patients requiring a primary TKA
- Male and nonpregnant female patients
- Between 18 and 80 years of age at time of surgery
- Patients with a diagnosis of osteoarthritis (OA), avascular necrosis (AVN), and not severe posttraumatic arthritis
- No previous osteosynthesis of the involved knee during the last 12 months
- Patients who understand the conditions of the study and are willing to participate for the length of the described follow up
- Patients who are capable of, and have given, informed consent for participation in the study

Exclusion

- Patients requiring revision surgery of a previous implanted total knee system
- Patients with a diagnosis of severe posttraumatic arthritis (TA) and rheumatoid arthritis (RA)
- Patients with active infection
- Patients with malignancy
- Patients with an immobile hip or ankle arthrodesis
- Severe obese patients (BMI > 35)
- Patients with a neurological deficit
- Previous history of unicompartmental knee arthroplasty or patellar prosthesis
- Patients with concurrent illnesses which are likely to affect their outcome

7 LENGTH OF SURVEILLANCE

The study has a follow up of 5 years. An inclusion period of 1,5 years is anticipated, so the study will run for 1,5 plus 5 years. When the inclusions start in June 2010, the study will end March 2016. The table below gives us an overview of the time window per visit.

VISIT	TIME WINDOW
Pre-op.	Date of or any time post the date of written informed consent up to the date of surgery.
Operation	N/A
PTD	N/A
6 weeks post-op.	± 1 week
12 weeks post-op	± 2 weeks
26 weeks post-op	± 2 weeks
1 year post-op	± 2 months
2 year post-op	± 2 months
5 years post-op	± 2 months

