3 OBJECTIVES

The primary objective is to compare the maximum flexion, both passive and active at every clinical follow-up time point up till 5 years postoperative, measured with a large goniometer. Our primary hypothesis is that the Scorpio NRG PS knee prosthesis has an average flexion of at least 7 degrees higher than the Scorpio PS knee prosthesis. Secondary objectives are to assess the complications, Chair raise test outcomes, knee pain (VAS) and surgery time. The secondary hypothesis is that there is no difference in complications and pain during the stair climb and chair raise test between the Scorpio NRG PS and the Scorpio PS. So more flexion does not result in more anterior knee pain. Also, the validity of computer navigated measurements and the relation between patella tilting and post-operative pain will be evaluated.

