11 PATIENT WITHDRAWALS

Every attempt must be made to ensure that all the patients return for all of the post-operative assessments. However, patients are free to withdraw from the Investigation at any time and are under no obligation to provide a reason for doing so. Patients who withdraw from the Investigation should have the reason for their withdrawal recorded on the case report forms (CRF's), if at all possible. All attempts should be made to ascertain whether any patient apparently lost to follow up has actually chosen not to return or is deceased.

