17 ETHICAL CONSIDERATIONS

Informed Consent

Prior to entry into the Surveillance the investigator (or nominated representative) will give the patient written (in native language of the patient) and verbal explanation of the nature of the study to an appropriate level of detail. The patient must give a written consent to participate in the study. Patients are invited to sign and date the consent form, indicating their consent for enrolment (Investigators may not date the consent form on the patient's behalf).

The investigator (or nominated representative) will also sign and date the Consent Form to indicate that the purpose, risks and benefits of the study were explained to the patient and their signature witnessed. The original signed Consent Form will be filed at the Investigational site.

Patients are free to withdraw from the Investigation at any time and are under no obligation to provide a reason for doing so. A clinical trial insurance and a liability insurance is arranged. An independent orthopaedic surgeon is appointed who is fully informed about this study but does not participate in the study.

Patients can, at any time, receive information about his/ her results.

The study will be performed according to the declaration of Helsinki, wet medisch-wetenschappelijk onderzoek met mensen and guidelines CCMO.

Stryker's local CRA will provide the MEC azM/UM with the following reports:

- An annual progress report
- An end-report, sent within 8 weeks after completion of the study
- An end-report containing the results and conclusions, sent within 1 year after completion of the study

Personal data protection

Stryker Europe affirms and upholds the principle of the patient rights to protection against invasion of privacy. All data recorded in the CRFs or used for further evaluation are coded by patient study number. Identification is restricted to authorized persons. In all data analyses the identity of patients will remain anonymous. Anonymous patient data may be stored and electronically processed by Stryker Europe for the purpose of scientific evaluation and may be forwarded to a company and/or an authority located in- and outside Europe for registration and/or marketing purposes. Only authorized representatives of Stryker Europe and health authorities will have allowed access to personal medical records for the sole purpose of checking the accuracy of data collected in the trial.

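### Does the March 2016 end date in Section 7, nine months short of the stated durations, threaten the 5-year follow-up?

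*Combined protocol and SAP*

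**What the plan says.** Section 7 (Length of Surveillance) gives the follow-up, "The study has a follow up of 5 years", and then the overall duration: "An inclusion period of 1,5 years is anticipated, so the study will run for 1,5 plus 5 years". The next sentence gives the calendar dates: "When the inclusions start in June 2010, the study will end March 2016". The table below it allows ±2 months around the 5-year visit.

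Other sections bear on what the end date could affect:

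- Section 3 sets the primary objective as a comparison of maximum flexion "at every clinical follow-up time point up till 5 years postoperative".
- Section 9.1.4 fixes the schedule by time since operation: "Patients will be assessed at post operative intervals at 6 weeks 3 months, 6 months 1, 2 and 5 years". Table 2 in Section 9 lists the same visits.
- Section 11 says of retention: "Every attempt must be made to ensure that all the patients return for all of the post-operative assessments".
- Section 17 times the reports to the ethics committee from the study's completion, for example: "An end-report, sent within 8 weeks after completion of the study".

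No other section gives a start or end date for the study.

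**The concern.** Two adjacent sentences in Section 7 cannot both be right, and the gap is too large for rounding. The end date is also the only one in the document, so a reader looking for the close of data collection would find March 2016.

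The 5-year visit is where an early close would be felt. It is the last of the time points in the primary objective, and Section 15 plans a separate 5-year paper. If collection really stopped in March 2016 after 18 months of inclusion, the patients operated on later could not have that visit. The 5-year comparison would then rest on the earlier-enrolled patients only, with fewer than the 40 per group that Section 6.1 calls for. A reader might also count the Section 17 reporting deadlines from the wrong month.

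**Working it through.** **Inputs, all from Section 7:** start June 2010; inclusion 1.5 years = 18 months; follow-up 5 years = 60 months; 5-year window ±2 months; stated end March 2016.

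**Reproducing the stated end.**

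- Planned length: 18 + 60 = 78 months.
- Last inclusion: June 2010 + 18 months = December 2011.
- Last 5-year visit: December 2011 + 60 months = December 2016. With the window it falls between October 2016 (76 months from the start) and February 2017 (80 months).
- June 2010 to March 2016: 5 years and 9 months = 69 months.
- Shortfall: 78 − 69 = 9 months.

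March 2016 is not reproduced.

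**Whether another way of counting closes the gap.**

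- Early edge of the window: by March 2016 a patient included in December 2011 has 69 − 18 = 51 months of follow-up. The window opens at 58 months, in October 2016, 7 months later.
- June 2010 counted as the first month of inclusion, with the last visit at the early edge: September 2016, still 6 months late.
- Counting from surgery instead of consent: surgery follows consent, so this can only move the end later.

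**Which figure would have to change.** Any one of three would reconcile them:

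| Figure changed | Value needed |
|---|---|
| End date | December 2016 |
| Start date | September 2009 (+ 78 months = March 2016) |
| Inclusion period | 69 − 60 = 9 months, or 88/9 = 9.8 patients a month against 88/18 = 4.9 |

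The text does not say which is meant.

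**Size if March 2016 were a cut-off (hypothetical).** Assume enforcement in March 2016 and uniform accrual over 18 months. Neither is stated in the documents. In whole months, patients included in the first 9 of 18 months reach 60 months, so 88 × 9/18 = 44 do not. Accepting visits at 58 months extends this to the first 11 months, so 88 × 7/18 ≈ 34 do not. Varying the exact start and end days within the stated months widens the range to about 29 to 49. These counts use all 88 enrolled, including those whom Section 6.1 already expects to lose through its 10% allowance.

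Earlier visits are safe even then. The last 2-year visit falls at December 2011 + 24 months = December 2013, or February 2014 with the window.

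**Whether anything in the plan uses the date.**

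- Visits: Section 2.3, the Section 7 window table, Table 2 and Section 9.1.4 all count from the operation.
- Enrolment: the Study Design Summary has it continue until the group size of 88 is reached, and Section 7 calls the 1.5 years anticipated. The end date is therefore a projection that moves with accrual.
- Sample size: Section 6.1 uses a 7-degree difference, an SD of 11, 80% power, a two-sided alpha of 0.05 and 10% loss. No calendar date enters.
- Analysis: Sections 14 and 14.1 set no data cut-off or database-lock date.
- Reporting: Section 17 counts from an event, not from a month.

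**The case for a change.** The strongest case for acting is that the error is certain, can be seen from Section 7 alone, and would take a line to correct. Section 7 is the only place that dates the end of the study, and no section defines what completing it means. Someone relying on the one date given could set the two Section 17 deadlines nine months early, before the last 5-year visits. Patients are also asked at inclusion to commit to the described length of follow-up, so that description ought to be consistent.

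The discrepancy itself stands in full. The consequences do not follow from it. A mistaken forecast does not move a deadline that runs from an actual event: while 5-year visits are outstanding, the study is not complete on any ordinary reading. The commitment asked of each patient is 5 years from surgery, and that is stated consistently throughout. Losing a third to just over a half of the patients at 5 years requires someone to enforce March 2016 against the visit schedule and against Section 11. No section asks for that.

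**Conclusion.** The dates in Section 7 are inconsistent by nine months (69 against 78), and the visit window does not absorb the difference. The documents do not allow one to say which of the three figures is wrong. December 2016 is the end only if the June 2010 start and both durations stand.

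No change to the plan follows. The slip is clerical and sits in a projected date that no procedure uses. Anyone running the study from the visit schedule would see each patient at 5 years whatever that sentence says. No patient is lost because of this date; the 10% loss to follow-up in Section 6.1 is a separate allowance. Reconciling the figures at a routine edit would be harmless, but it would leave the visits, sample size, analysis and conclusions as they are.

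This rests on March 2016 not being applied as a stop to data collection. The supplied text supports that reading: it nowhere names the date as a cut-off, and it schedules the 5-year visit for every patient.
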